### 3.1.2. OPEN-LABEL EXTENSION

Subjects who complete the DB treatment during the Main Study are eligible to enter a 24-week OLE, which consists of the following:

- OLE Period for 24 weeks
- OL Safety Follow-up Period for 2 weeks

During this period subjects will receive OL JZP-258.

Subjects will be eligible to enter the OLE if they meet all eligibility criteria and their treatment status is:

- Completed DB treatment in the Main Study and rolling over into OLE
- Completed the Main Study and currently treated with Xyrem alone or Xyrem plus an additional antiepileptic
- Completed the Main Study and currently treated with a non-Xyrem antiepileptic
- Completed the Main Study and not currently receiving treatment

#### *Open-Label Extension Period*

Subjects can enter the OLE directly from the Main Study (enter at Visit 16) or after completion of the Main Study (enter at Visit 18).

- **Rollover Subjects:** those who enter the OLE at Visit 16 (i.e., “rollover” directly from the Main Study). Their Visit 16 will have the dual purpose of being the last day on the Main Study and Day 1 for the OLE.
- **Re-entry Subjects:** those who enter the OLE following completion of the Main Study (i.e., require “re-entry” into the study). Their Open-Label Extension Day 1 is at Visit 19 and they undergo Open-Label screening at Visit 18.

[figure not shown]
Prior to any study activity, informed consent for the OLE will be obtained.

#### *Open-Label Safety Follow-up Period*

Subjects will return for a Safety Follow-up visit 2 weeks after completion or early termination of the OLE period.

A study diagram for the OLE is presented in [Figure 1](#).

Figure 2 Study Diagram for Open-Label Extension

## 3.2. BLINDING

The OTTP, SDP, and OLE Periods of this study will not be blinded to the subjects or to the study personnel. A DB approach will be used during the RWP. JZP-258 and JZP-258 placebo oral solution will be matched in volume, to ensure adequate blinding of the subject and study personnel during the RWP.

## 3.3. TREATMENT ASSIGNMENT AND RANDOMIZATION

JZP-258 and matching placebo will be provided to subjects as an oral solution 0.5 g/mL. The volume of solution dispensed and returned will be recorded on the investigational medicine record. Study drug will be administered as described above:

### *Open-Label Optimized Treatment and Titration Period*

During the OL OTTP all subject will receive OL JZP-258.

**Pre-randomization Groups 1 and 2:** These subjects will be switched from their current dose of Xyrem to JZP-258 on a gram (g) to g straight conversion at the start of the OL OTTP and remain on that dose for 2 weeks. If further titration is needed, titration will proceed at a rate of 1 or 1.5 g per night per week during this period not to exceed a total dose of 9 g per night.

**Pre-randomization Groups 3 and 4:** These subjects will receive an initial dose of JZP-258 of 4.5 g per night at the start of the OL OTTP. Dose adjustments will proceed at a rate of 1 or 1.5 g per night per week until a tolerable dose of JZP-258 is reached over a period of 2 weeks. If needed, the dose of JZP-258 may be further titrated to a stable, tolerable, and effective dose that does not exceed a total dose of 9 g per night.

With the following exception, all groups should dose with JZP-258 orally in two equally divided doses taken at bedtime and again 2.5 to 4 hours later. Subjects who entered the study on Xyrem (Pre-randomization Groups 1 and 2) and have used a different nightly dosing regimen prior to study entry, may continue their pre-study dosing regimen throughout the study (i.e., the dosing regimen may consist of two or three equally or unequally nightly divided doses and dosing may begin after the first nightly awakening; however, a once nightly dosing will not be permitted during the study). Subjects entering the study on a different nightly dosing regimen may not change their regimen during the study.

### *Open-Label Stable-Dose Period*

During the OL SDP subjects will receive OL JZP-258 at the same unchanged dose that they received during the last 2 weeks of the OL OTTP.

### *Double-Blind Randomized-Withdrawal Period*

At the beginning of the DB RWP, subjects will be randomized 1:1 to receive one of the following two treatments during the 2-week DB RWP and randomization will be stratified based on each subject's Pre-randomization Group, as defined at study entry:

**JZP-258:** JZP-258 will be continued as a double-blind treatment at the stable dose taken during

the OL SDP.

**Placebo:** Placebo will be initiated as a double-blind treatment at a volume equivalent to the JZP-258 dose taken during the OL SDP.

A statistician selected by Jazz will prepare and retain the master randomization code for the entire study. This statistician will not be involved in the analysis of this study. The randomization codes will be generated and retained according to Jazz Standard Operating Procedure on the generation, distribution, and access to randomization information for clinical studies. Unless there is an emergency that requires the release of the subject's assigned treatment, the code will not be broken or released until study data are collected and accepted for analysis.

The Investigator will access an Interactive Web Response System (IWRS) to randomize subjects.

#### *Open Label Extension*

During the OLE all subjects will receive OL JZP-258.

**Rollover Subjects:** Subjects entering directly from the Main Study will be started at a dose no higher than the dose they received at the end of the OL SDP. A lower starting dose will be allowed at the discretion of the Investigator. If further titration is required, it will proceed at a rate of 1 or 1.5 g per night per week during this period, not to exceed a total dose of 9 g per night.

**Re-entry Subjects on Xyrem (alone or with an additional antiepileptic):** Subjects re-entering the study during the OLE on Xyrem alone or on Xyrem plus an additional antiepileptic will be switched from their current dose of Xyrem to JZP-258 on a g to g straight conversion at the start of the OLE. If further titration is required, it will proceed at a rate of 1 or 1.5 g per night per week during this period, not to exceed a total dose of 9 g per night.

**Re-entry Subjects on non-Xyrem Antiepileptic or Not Currently Receiving Treatment:** Subjects re-entering the study receiving treatment with a non-Xyrem antiepileptic only or not treated with any antiepileptic agent will receive an initial dose of JZP-258 of 4.5 g per night at the start of the OLE. Dose adjustments will proceed at a rate of 1 or 1.5 g per night per week until a tolerable dose of JZP-258 is reached. If needed, the dose of JZP-258 may be further titrated to a stable, tolerable, and effective dose that does not exceed a total dose of 9 g per night.

### **3.4. SAMPLE SIZE JUSTIFICATION**

Up to 185 subjects will be enrolled in the study to ensure a minimum of 130 subjects (65 subjects per treatment group) enter the DB RWP. This includes at least 50 subjects on Xyrem and 60 subjects using Xyrem plus other antiepileptics or non-Xyrem antiepileptic alone, as applicable.

A sample size of 65 subjects randomized per treatment group will provide at least 90% power to detect a difference in the change in mean weekly cataplexy attacks, from the OL SDP to the DB RWP, of 17.5 between JZP-258 and placebo. This assumes a common standard deviation (SD) of 30 and a two-sided significance level of 0.05 using a t-test. Assuming a 30% dropout rate prior to randomization, approximately 185 subjects will be enrolled to ensure that a minimum of 130 subjects enter the DB RWP. Assumptions were conservatively based on previous completed Xyrem studies GHB-2, OMC-SXB-15, and OMC-SXB-21 and account for study design. From these 3 studies, the mean weekly reduction in cataplexy attacks of Xyrem compared to placebo (common SD) ranged from approximately 10 (30) to 16 (28).

### **3.5. SCHEDULE OF EVENTS**

Refer to Appendix 1 of PA 5 for the schedule of events for the Main Study and for the OLE.

### **3.6. CHANGES TO ANALYSIS FROM PROTOCOL**

For the purpose of the main efficacy analysis (primary and all secondary endpoints), the Baseline Observation Carried Forward (BOCF) method will be used to impute missing results for subjects without post-randomization data. The PA 5 does not suggest any specific methodology and the study team agreed to apply the BOCF approach.

## **4. PLANNED ANALYSES**

### **4.1. DATA SAFETY MONITORING BOARD**

A data safety monitoring board is not planned for this study.

### **4.2. INTERIM ANALYSIS**

There will be no interim analysis for this study. As specified in PA 5, Section 9.15, the sponsor has taken the decision not to perform the interim analysis due to it not being operationally feasible as full study recruitment has been achieved faster than originally anticipated.

### **4.3. ANALYSIS AT THE END OF THE MAIN STUDY**

The final efficacy analysis and a safety analysis of available data will be performed after all subjects have completed or early terminated from the Main Study.

All the analysis will be performed by [REDACTED] following sponsor approval of this SAP, sponsor approval of the list of major protocol deviations potentially having an impact on efficacy data, sponsor approval of the analysis populations, data extraction (soft DBL), and unblinding of the study.

### **4.4. ANALYSIS AT THE END OF STUDY**

The final safety analysis will be performed after all subjects have completed or early terminated from the OLE.

The final, planned safety analyses of the OLE identified in this SAP will be performed by [REDACTED]

following sponsor approval of this SAP and DBL.

## 5. ANALYSIS POPULATIONS

### 5.1. ALL SCREENED SUBJECTS POPULATION

The all screened subjects population (SCR) will contain all subjects who provided informed consent for this study.

This analysis population will be used to summarize the number of screened, screen failure and enrolled subjects.

### 5.2. ALL ENROLLED SUBJECTS POPULATION

For the analysis purposes, the all enrolled subjects population (ENR) will contain all subjects who provided informed consent for this study and were deemed as meeting the inclusion/exclusion criteria of this study by the Investigator before taking the first dose of study drug or received at least one dose of study drug.

This analysis population will be used to summarize subject disposition, major protocol deviations as classified in CTMS, and inclusion/exclusion from the analysis populations as well as reasons for exclusion from each analysis population. Unless otherwise specified, summaries will be presented overall and by the Pre-randomization Group.

### 5.3. SAFETY POPULATION

The overall safety population (SAF) will include all subjects who took at least one dose of study drug. The safety population will also be defined for each study period:

- **For the OL Optimized Treatment and Titration Period**, the OTTP SAF will contain all subjects in the ENR who took at least one dose of OL study drug during the OL OTTP. Hence, the SAF population for the OL OTTP will be the same as the overall SAF.
- **For the OL Stable-Dose Period**, the SDP SAF will contain all subjects in the ENR who took at least one dose of OL study drug during the OL SDP.
- **For the DB Randomized-Withdrawal Period**, the RWP SAF will contain all subjects in the ENR who took at least one DB study drug.
- **For the OLE Period**, the OLE SAF will contain all subjects in the ENR who took at least one dose of OL study drug during the OLE Period.

SAF will be used to summarize subjects' demographic and other baseline characteristics data, past medical conditions/diseases, surgical history, concurrent medical conditions/disease, disease history data as well as exposure to study drug and all safety data.

The SAF, SDP SAF, RWP SAF, and OLE SAF will be used to summarize concomitant medications by study period i.e. OTTP, SDP, DB RWP, OLE respectively.

Summaries based on SAF, OTTP SAF, SDP SAF, OLE SAF will be presented overall and by Pre-randomization Group.

Summaries based on RWP SAF will be presented overall and by treatment group. For these summaries, subjects will be classified according to treatment actually received during the DB RWP. In other words, subjects who receive at least one kit containing active JZP-258 during the DB RWP will be considered as having received JZP-258 during the period. Subjects who receive only placebo during all the DB RWP will be considered as having received placebo during this period.

#### **5.4. ALL RANDOMIZED SUBJECTS POPULATION**

The all randomized subjects population (RND) will include all randomized subjects.

Subject disposition for the DB RWP as well as analysis population for the DB RWP will also be summarized using this analysis population. Summaries will be presented overall and by randomized treatment group.

#### **5.5. EFFICACY POPULATION**

The efficacy population (EFF) will contain all randomized subjects who have received at least one 1 dose of DB study drug and have at least one set of post-randomization efficacy data. A set of efficacy data includes at least one of each of the following efficacy assessments: Cataplexy, ESS, PG1c, CG1c, SF-36 and EQ-5D-5L. This population will be used as the main analysis population for the primary and secondary efficacy endpoints. Demographics and other baseline characteristics data, past medical conditions/diseases, surgical history, concurrent medical conditions/disease, disease history and exposure to study drug data will also be summarized using this analysis population. For summaries and analyses presented based on the EFF, subjects will be classified according to randomized treatment group.

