## 6.2. BASELINE

- **Weekly average of Cataplexy Attacks:** For this efficacy endpoint, baseline will be defined as the average number of daily cataplexy attacks from days with non-missing data within the 2 weeks OL SDP, multiplied by 7.

- **Epworth Sleepiness Scale (ESS), 36-Item Short Form Health Survey (SF-36), and European Quality of Life (EuroQoL) 5 Dimensions 5 Levels (EQ-5D-5L):** For these assessments, baseline will be defined as the last non-missing measurement taken prior to or on the date of randomization (including unscheduled assessment) i.e., DB RWP Day 1.
- **Clinician Global Impression of Severity (CGIs) for Narcolepsy Overall:** For this assessment, no baseline will be defined as this scale will be collected only once during the study i.e., at the end of the OL SDP.
- **Patient Global Impression of Change (PGIc) for Narcolepsy Overall and Clinician Global Impression of Change (CGIc) for Narcolepsy Overall:** For these assessments, no baseline will be defined as these scales already assess the change in the severity of the subject’s narcolepsy overall since the end of the OL SDP. Furthermore, these assessments will be recorded only once during the study, i.e., at the end of the DB RWP.
- **Hematology, Fasting Chemistry (incl. electrolytes), Weight, Vital signs, Urine Drug Screen, Columbia-Suicide Severity Rating Scale (C-SSRS), Physical Examination, 12-Lead Electrocardiogram (ECG) and Patient Health Questionnaire-9 (PHQ-9):** For these assessments, two types of baseline will be defined:
  1. ‘Main Study baseline’ will be defined as the last non-missing measurement collected/ assessed prior to or on the same day of the first dose of study drug during the Main Study, including unscheduled measurements and retests.
  2. ‘OLE baseline’ will be defined as the last non-missing measurement collected/ assessed prior to or on the same day of the first dose of study drug during the OLE, including unscheduled measurements and retests.

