## 9.8. EFFICACY OUTCOMES

All efficacy analyses will be performed with the EFF, unless otherwise indicated.

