## 9.8.1. PRIMARY EFFICACY ENDPOINT

### 9.8.1.1. PRIMARY EFFICACY ENDPOINT & DERIVATION

The primary efficacy endpoint is the change in average weekly number of cataplexy attacks from the two weeks of the OL SDP to the two weeks of the DB RWP.

Subjects will complete a daily cataplexy frequency diary each night prior to bedtime to record the number of cataplexy attacks that they had that day beginning at Study Day 1 up to the end of the DB RWP visit. Daily cataplexy frequency diary will not be collected during OLE.

For subjects with at least one day of cataplexy attack data, the average weekly number of cataplexy attacks over each of the two weeks (see Table 1) of the OL SDP will be calculated as follows:

$$\frac{\text{Total number of cataplexy attacks within the OL SDP period}}{\text{Number of days with non-missing data within the OL SDP period}} \times 7 \text{ days}$$

Average weekly number of cataplexy attacks over each of the two weeks of the DB RWP will be calculated similarly. Additionally, average weekly number of cataplexy attacks by week for each study period (see Table 1) will also be calculated as follows:

$$\frac{\text{Total number of cataplexy attacks within a week}}{\text{Number of days with non-missing data within that week}} \times 7 \text{ days}$$

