### 9.8.1.3. MISSING DATA METHODS FOR PRIMARY EFFICACY ENDPOINT

For subjects without post-randomization daily cataplexy attack data, the average weekly number of cataplexy attacks from the OL SDP will be carried forward using a BOCF approach.

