#### **9.8.2.2. MISSING DATA METHODS FOR KEY SECONDARY EFFICACY ENDPOINT**

For subjects without post-randomization ESS data, the result from the OL SDP will be carried forward using a BOCF approach.

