#### **9.8.2.4. SENSITIVITY ANALYSIS OF KEY SECONDARY EFFICACY ENDPOINT**

Sensitivity analyses will be performed similarly to the primary efficacy endpoint (see [section 9.8.1.5](#)). The sensitivity analysis to the missing data assumption using LOCF will not be performed as only one post-randomization ESS assessment was performed.

An additional sensitivity analysis to the use of stimulant during the OL SDP will be performed using the same ANCOVA model as for the primary efficacy endpoint, but adjusted for the stimulant use i.e., a binary

variable (“yes” if the subject takes at least one dose of stimulant during the SDP, “no” otherwise) will be added to the model as a covariate. Stimulant medications are listed in [APPENDIX 3](#).

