**9.8.3.2. MISSING DATA METHODS FOR OTHER SECONDARY EFFICACY ENDPOINTS**

**9.8.3.2.1. PGIC AND CGIC FOR NARCOLEPSY OVERALL AT THE END OF THE DB  
 RANDOMIZED-WITHDRAWAL PERIOD**

Missing data will not be imputed for these other secondary efficacy endpoints.

**9.8.3.2.2. CHANGE IN SF-36 AND IN EQ-5D-5L SELF-REPORTED QUESTIONNAIRE FROM END OF OL STABLE-DOSE PERIOD TO END OF DB RANDOMIZED-WITHDRAWAL PERIOD**

For subjects without post-randomization SF-36 scale normalized scores and 2 overall components as well as EQ-5D-5L dimension and VAS scores, the result from the OL SDP will be carried forward using a BOCF approach.

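### The Efficacy Population requires a post-randomization record on all six efficacy instruments, so subjects with observed cataplexy diaries can be dropped and the primary endpoint's BOCF rule has no one to act on

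*SAP*

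**What the plan says.** Protocol 9.4 conditions the Efficacy Population on one set of post-baseline efficacy assessments and does not say what a set is. SAP 5.5 supplies the definition: "A set of efficacy data includes at least one of each of the following efficacy assessments: Cataplexy, ESS, PG1c, CG1c, SF-36 and EQ-5D-5L". SAP 9.8 then states: "All efficacy analyses will be performed with the EFF, unless otherwise indicated".

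The endpoint sections are written for a population in which an instrument can be absent:

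- **Primary endpoint, derivation (SAP 9.8.1.1):** the weekly rate is computed "For subjects with at least one day of cataplexy attack data".
- **Primary endpoint, missing data (SAP 9.8.1.3):** "For subjects without post-randomization daily cataplexy attack data, the average weekly number of cataplexy attacks from the OL SDP will be carried forward". SAP 3.6 lists BOCF as the one declared change from the protocol.
- **Key secondary endpoint (SAP 9.8.2.2):** "For subjects without post-randomization ESS data, the result from the OL SDP will be carried forward using a BOCF approach".
- **PGIc and CGIc (SAP 9.8.3.2.1):** "Missing data will not be imputed for these other secondary efficacy endpoints".
- **SF-36 and EQ-5D-5L (SAP 9.8.3.2.2):** BOCF when post-randomization scores are absent.

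On timing, SAP 6.2 says of PGIc and CGIc that "these assessments will be recorded only once during the study, i.e., at the end of the DB RWP", and SAP 9.8.2.4 notes that "only one post-randomization ESS assessment was performed". Protocol 6.12.5 and 6.12.6 place the only post-randomization SF-36 and EQ-5D-5L at Visit 16 or early termination.

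**The concern.** The definition makes entry to the primary analysis set depend on a complete battery at one visit, and four of the required forms are neither the primary nor the key secondary endpoint. A subject who kept the cataplexy diary for all 14 double-blind days but did not return, say, the EQ-5D-5L is excluded from the cataplexy analysis. Subjects who leave without a full final visit are the most likely to be affected, and they are the ones the missing-data rules were written for.

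The population definition and the endpoint-level rules cannot both operate as written. A programmer would have to choose between them, and that choice about the primary analysis set should be recorded before unblinding. The planned robustness check is also exposed, because its trigger is counted in the same set.

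**Working it through.** **Population definition against each missing-data rule**

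| Rule | Whom it addresses | Can such a subject be in the EFF? |
|---|---|---|
| Cataplexy BOCF (9.8.1.3) | no post-randomization diary | No: a post-randomization cataplexy record is required |
| ESS BOCF (9.8.2.2) | no post-randomization ESS | Only if a form was returned with three or more blank items (9.8.2.1) |
| PGIc/CGIc left missing (9.8.3.2.1) | PGIc or CGIc missing | No: both are required |
| SF-36/EQ-5D-5L BOCF (9.8.3.2.2) | no scores | Only if a returned form is unscorable or partly blank |

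**Does another analysis bring the excluded subjects back?** No. The Per Protocol population is a subset of the EFF (SAP 5.6). The All Randomized population serves disposition and population summaries (SAP 5.4). The sensitivity-analysis trigger is counted in the EFF (SAP 9.8.1.5).

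**The plan's own power figure.** Inputs from SAP 3.4: 65 per arm, difference 17.5, SD 30, two-sided 0.05, t-test. The noncentrality is 17.5 / (30 × √(2/65)) = 3.33 on 128 df, giving power 0.910. The stated 90% reproduces. The smallest n per arm that keeps 90% by t-test is 63. At 62 per arm (three lost), noncentrality is 3.25 on 122 df and power is 0.897.

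The documents give no rate of missing final-visit forms. Everything below uses assumed inputs.

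**Full-diary subjects excluded.** If each of the five visit-based forms is missed with probability p, the excluded share lies between p (always the same subjects) and 1 − (1 − p)^5 (independent misses):

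- p = 0.5%: 0.5% to 2.5%
- p = 1%: 1% to 4.9%, or 1.3 to 6.4 of 130
- p = 2%: 2% to 9.6%

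**The 5% trigger.** More than 5% of 130 (6.5) means at least 7 subjects. Take 7 early leavers with no Week 2 diary data:

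- counted in all 130: 7/130 = 5.4%, trigger fires
- one of the seven lacks a Visit 16 or early-termination form: 6/129 = 4.65%, does not fire
- all seven lack one: 0/123 = 0%, does not fire

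**Effect on the estimated difference.** Assume true mean changes of 0 on JZP-258 and +17.5 on placebo. Let a fraction f of one arm, with mean change m, be excluded.

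- Placebo subjects excluded: difference = (17.5 − f·m)/(1 − f). With m = +35, f = 2%, 5%, 10% gives 17.1, 16.6, 15.6. At f = 10%, m = +25 or +50 gives 16.7 or 13.9. If these subjects have diaries, analysing them restores 17.5.
- JZP-258 subjects excluded, f = 10%, m = +17.5: retained mean = −1.75/0.9 = −1.94, so the difference is 19.44.

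**Leavers with no diary at all (f = 10%).** Enlarging the set does not repair this case, because BOCF assigns them zero change. For placebo leavers at +35, BOCF gives 0.9 × 15.56 = 14.0, against 15.6 when they are excluded. For JZP-258 leavers at +17.5, BOCF gives 17.5 + 0.9 × 1.94 = 19.25, against 19.44.

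**The case against.** The strongest reply is that this is a drafting slip. SAP 5.5 has other typographical errors, and the endpoint rules plainly expect EFF members who lack an instrument. If *any* was meant where *each* was written, endpoint-level BOCF works for everyone except subjects with no efficacy data at all. That may well be the intent, but nothing in the SAP says so, and the text would still need correcting.

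The numbers may also be very small. The double-blind period lasts two weeks, SAP 9.8.1.5 expects discontinuation to be rare, and Protocol 6.14.1 and 6.14.2 ask early terminators to complete the final-visit assessments; those who do remain in the EFF. SAP 9.1 reports exclusions by randomized arm. All of this stands as a limit on size. It does not remove the defect: the assessments are requested and cannot be guaranteed, and a table of exclusions does not return anyone to the analysis.

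Two criticisms of the illustrations are fair. Forms collected at one visit are likely to be missed together, so the lower bounds are the more plausible, and 10% exclusion is an extreme case. If the residuals fail the normality test, the primary test is rank-based, so the shifts in means do not carry over directly.

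Unscheduled visits could in principle supply a form, but the schedule does not provide for this. The averaging of available diary days still operates for EFF members; only the BOCF component is left without subjects.

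Finally, the narrower change of *each* to *any* would stay within Protocol 9.4. It would still leave out dosed subjects with no efficacy data, whom SAP 3.6 says BOCF is meant to cover.

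**Conclusion.** The concern holds on the text. The all-six requirement conflicts with the SAP's own rules for cataplexy, PGIc and CGIc, and leaves those for ESS, SF-36 and EQ-5D-5L almost no scope. It can remove observed primary-endpoint data because an unrelated form is missing. The SAP's description of its primary missing-data handling as conservative rests on a BOCF step that would not be applied to anyone.

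The size is not known. The design has room to lose two subjects per arm before power drops below 90%, and losing three costs 1.3 percentage points (91.0% to 89.7%). The direction of any bias depends on who is excluded: in the illustrations, excluding worsening placebo subjects shrinks the difference and excluding worsening JZP-258 subjects enlarges it. These figures rest on assumed loss rates and mean changes. The conflict between the definition and the rules does not. It should be fixed before unblinding.

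**What to change.** In SAP 5.5, delete the requirement for a record on each instrument and define the EFF as all randomized subjects who received at least one dose of double-blind study drug. Apply each endpoint's existing missing-data rule in that set. Count the existing 5% trigger there too, and run the existing control-based multiple imputation in that set when it fires. Record the departure from the post-baseline condition of Protocol 9.4 in SAP 3.6.

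The cost is one definition, one entry in SAP 3.6 and the analysis-set programming. No new data or method is needed. There are two drawbacks: the estimate may be slightly smaller where BOCF now applies, and subjects with no diary at all are still handled by a single imputation in the primary analysis. For them the gain is that the stated rule is actually applied and the planned multiple imputation can include them.
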